3.4.3 Replacement policy

Subjects who withdraw from the study will not be replaced.

3.4.4 Stopping criteria

Dosing will be stopped in case of an unacceptable tolerability profile based on the nature, frequency, and intensity of observed AEs judged jointly by the investigator and the sponsor or as recommended by the DMC.

In the event of a study hold due to unacceptable tolerability, the sponsor will conduct an extensive safety and PK analysis and will communicate to stakeholders, including the Investigators, institutional review boards (IRBs)/independent ethics committees (IEC), and health authorities any potentially emergent safety information as well as the timing of planned resumption of dosing. Dosing and enrollment will not resume unless it is considered safe to do so after consultation with Investigators and health authorities and approval by IRBs/IECs.

Fulcrum Therapeutics
Protocol FIS-001-2020

Losmapimod

4 STUDY POPULATION

4.1 Inclusion criteria

Eligible subjects must meet all of the following inclusion criteria at screening.

1. Able and willing to provide written informed consent.
 - a. Note: Subject's legally authorized representative may provide informed consent as applicable based on local guidelines and regulations (see [Section 9.1.3](#)). If consent is obtained from a legally authorized representative, then assent should be obtained from the subject.
2. Willing and able to comply with all study procedures.
3. Age ≥ 40 years at time of screening.
4. Confirmed infection with SARS-CoV-2 virus at or before the baseline visit (by polymerase chain reaction [PCR] testing).
 - a. Note: Refer to the Study Manual for details on PCR SARS-CoV-2 testing procedures.
5. ≤ 7 days to the time of randomization from the time of collection of the specimen that tested positive for the SARS-CoV-2 virus.
6. Hospitalization at the time of the baseline visit.
7. Oxygen saturation $\geq 92\%$ at the baseline visit, which can be either on room air or on oxygen supplementation if using $\leq 10\text{LPM}$ by nasal prong or close-fitting mask.
8. Evidence of pulmonary involvement consistent with COVID-19 by either clinical examination or radiographic examination (whichever is per local standard of care), per the judgment of the investigator. Evidence of pulmonary involvement obtained by clinical examination should be documented in the eCRF.
9. Clinical syndrome consistent with COVID-19 at screening, per the judgment of the investigator ([CDC 2020](#)).
10. CRP at screening $>15 \text{ mg/L}$ (which is equivalent to $>1.5 \text{ mg/dL}$) on local laboratory testing.
11. Agrees to practice an approved method of birth control as follows (as applicable to local [country] guidelines and regulations for sites outside the US):
 - a. Females of childbearing potential: Using 1 of the following acceptable methods of contraception: surgical sterilization (eg, bilateral tubal ligation), intrauterine contraception/device, hormonal contraception, or any 2 barrier methods (a combination of male or female condom with diaphragm, sponge, or cervical cap). This criterion must be followed from the time of the first dose of study medication until 90 days after last dose
 - b. Males: Effective male contraception includes a vasectomy with negative semen analysis at follow-up, or the use of condoms. This criterion must be followed from the time of the first dose of study medication until 90 days after last dose.

Note: Abstinence can be considered an acceptable method of contraception at the discretion of the investigator. Periodic abstinence (eg, calendar, ovulation, symptothermal, post ovulation methods) and withdrawal are not considered acceptable methods of contraception.

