Version 3.0, 21 October 2020	
Inclusion criteria were updated as follows:
 
 The age in inclusion criterion 3 was changed from ≥ 50 years old to ≥ 40 years old based on clinical site feedback regarding recruitment challenges, while maintaining older age as an important risk factor for progression of COVID-19. Baseline oxygen requirements in inclusion criterion 7 were changed based on clinical site feedback to oxygen saturation $\geq 92\%$, which can be either on room air or on oxygen supplementation if using $\leq 10\text{L}/\text{min}$ by nasal canula or close-fitting face mask. The “note” for inclusion criterion 8 was combined into the main criterion 8 for optimal readability. 
Exclusion criteria were updated as follows:
 
 The definition of critical disease in exclusion criterion 2 was updated to remove “anticipated need for intubation” and “severe pulmonary involvement” based on clinical site feedback; ARDS and immediate need for intubation or mechanical ventilation were retained in the definition of critical COVID-19 disease. Evidence of pulmonary involvement remains in inclusion criterion 8. Exclusion criterion 5 was updated to note that the exclusion is for poorly controlled HIV and to allow for the inclusion of subjects with HIV if their CD4 counts are normal and they have been on a stable antiviral regimen and are anticipated to remain on that regimen for the duration of the study. 
The changes above were also applied where applicable in the descriptions of the study design and procedures.
 
Minor administrative/operational and typographical clarifications were made.

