⁴ PK assessments will be performed as a substudy in all sentinel subjects. For those subjects requiring dialysis, a single pre- and post-dialysis PK should be obtained for review by the DMC to decide if dose adjustment is needed. PK should be measured weekly for 2 weeks at C_{max} (4-5 hours post dose) for subjects with renal insufficiency when possible.

⁶ Assessments for clinical/respiratory status, progression, and safety serum chemistry and hematology tests to be performed and samples to be collected while hospitalized based on standard-of-care local laboratory assessments and after discharge from the hospital by home visit or outpatient clinic visit or telemedicine call. For subjects who are discharged to home or other outpatient setting after initial hospitalization, the assessments and laboratory samples can be obtained less often but not less than at least once weekly. CRP result required to determine eligibility are based on local laboratory results at screening.

⁷ Viral load testing will be collected daily for the first 4 days using central testing in the first 10 enrolled subjects as part of the sentinel safety assessment at select sites. For all subjects, including the sentinel subjects, swabs, saliva, or other sample collection (as specified in the Study Manual) for central viral load testing will be collected on D1 pretreatment and on D7 or earlier if being discharged from the hospital prior to D7.

Fulcrum Therapeutics
Protocol FIS-001-2020

Losmapimod

⁸ Vital signs will be performed after subjects have been supine for at least 5 minutes when possible. Vital signs to include oxygen saturation; PaO₂ should be recorded if available from blood gases obtained as part of SOC; oxygen administration should also be recorded (eg, room air or oxygen flow by nasal canula or facial mask or endotracheal tube). For subjects who are discharged to home or other outpatient setting after initial hospitalization, assessments may be obtained less often but at least once per week in the outpatient clinic or at home.

⁹ Height assessed at screening only; can be by self-report or from medical records. Weight is an actual recording.

¹⁰ Urinalysis will be performed during the study period only on Day 7 and on any other day only if clinically indicated.

¹¹ Pregnancy testing to be conducted within 72 hours of the first dose of study treatment.

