5.4 Treatment assignment and blinding

5.4.1 Randomization and treatment assignment

A total of up to 410 subjects will be recruited into this study and will be randomized in a 1:1 ratio to 15 mg losmapimod (BID) or placebo using an interactive/web voice response system (IxRS) for randomization. The randomization list will be produced by a qualified randomization vendor and will be stratified by age (<65 or ≥65) and requirement for oxygen at randomization (yes/no) at enrollment.

Fulcrum Therapeutics
Protocol FIS-001-2020

Losmapimod

Only subjects who have completed screening assessments and are eligible for participation in the study will be randomized to receive study drug. Randomized subjects will be sequentially assigned a unique subject number from the randomization list per the IxRS. From the time of randomization and throughout the duration of the study, subjects will be identified by their unique randomization number.

The authorized site personnel will prepare the appropriate study drug for each subject based on the randomization schedule. Treatment codes should not be broken except in emergency situations, ie, when knowledge of the treatment is essential for the immediate further management of the subject.

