6.3.1 Respiratory failure and survival assessment

Total number of study days free of oxygen supplementation and total number of study days free of respiratory failure will be evaluated. Refer to [Section 6.5.1](#) for further details of vital sign collection.

- Note: Respiratory failure is defined as either need for mechanical ventilation (invasive or non-invasive) or high flow oxygen (defined by greater than 15 LPM flow of oxygen to maintain oxygen saturation between 90% and 95%), sustained for at least 48 hours, at any time during the study.

The reason for hospitalization and number of total study days of hospitalization and intensive care unit (ICU) utilization will be recorded.

Details of subject discharge (date of discharge and condition at discharge) from the hospital will be recorded.

Any significant deviation from standard of care due to limited resources will be documented.

Survival status at the end of the study period will be documented, including cause of death for any reason.

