4 STUDY POPULATION

4.1 Inclusion criteria

Eligible subjects must meet all of the following inclusion criteria at screening.

1. Able and willing to provide written informed consent.
 - a. Note: Subject's legally authorized representative may provide informed consent as applicable based on local guidelines and regulations (see Section 9.1.3). If consent is obtained from a legally authorized representative, then assent should be obtained from the subject.
2. Willing and able to comply with all study procedures.
3. Age ≥ 50 years at time of screening.
4. Confirmed infection with SARS-CoV-2 virus at or before the baseline visit (by polymerase chain reaction [PCR] testing).
 - a. Note: Refer to the Study Manual for details on PCR SARS-CoV-2 testing procedures.
5. ≤ 7 days to the time of randomization from the time of collection of the specimen that tested positive for the SARS-CoV-2 virus.
6. Hospitalization at the time of the baseline visit.
7. $\geq 90\%$ oxygen saturation on room air and/or $\geq 94\%$ oxygen saturation on oxygen administration at 2 L/min by nasal canula at the baseline visit.
8. Radiographic (X-ray or computed tomography scan, per local standard of care) evidence of pulmonary involvement consistent with COVID-19 at screening or baseline, per the judgment of the investigator.
 - a. Note: If radiography is not considered local standard of care for COVID-19 diagnosis, evidence of pulmonary involvement consistent with COVID-19 may also be obtained from clinical examination, per the judgment of the investigator. Evidence of pulmonary involvement obtained by clinical examination should be documented in the eCRF.
9. Clinical syndrome consistent with COVID-19 at screening, per the judgment of the investigator ([CDC 2020](#)).
10. CRP at screening >15 mg/L (ie, >1.5 mg/dL) on local laboratory testing.
11. Agrees to practice an approved method of birth control as follows (as applicable to local [country] guidelines and regulations for sites outside the US):
 - a. Females of childbearing potential: Using 1 of the following acceptable methods of contraception: surgical sterilization (eg, bilateral tubal ligation), intrauterine contraception/device, hormonal contraception, or any 2 barrier methods (a combination of male or female condom with diaphragm, sponge, or cervical cap). This criterion must be followed from the time of the first dose of study medication until 90 days after last dose

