3.4 Efficacy Assessment

3.4.1 Primary Efficacy Endpoint

3.4.1.1 Primary Analysis

The primary efficacy endpoint is the proportion of subjects who progress to death or respiratory failure by Day 28.

Respiratory failure is defined as either need for mechanical ventilation (invasive or non-invasive) or high flow oxygen (defined by greater than 15 LPM flow of oxygen to maintain oxygen saturation between 90% and 95%), sustained for at least 48 hours, at any time during the study.

The fitted logistic regression model is used to predict the response rate for every subject in the study as if they had received the treatment or the control intervention.

Assuming p_t is probability of outcome in the losmapimod arm; p_c is the probability of outcome in the control arm

Study hypothesis: $H_0: p_t - p_c = 0$

$H_1: p_t - p_c < 0$

Assuming $p_t=0.18$, $p_c=0.30$, we can restate the hypothesis as

$H_0: \theta = \theta_0 = 0$

$H_1: \theta = \theta_1 = -0.12$

where θ is calculated as $p_t - p_c$. For the final analysis, the proportion of subjects achieving the primary endpoint in the treatment arms will be compared using an adjusted risk difference obtained from the logistic regression model, adjusted for stratification factors, sex, and baseline CRP. Sample SAS codes are provided in Appendix A. More details can be found in Guo et al. (2012) and Ge et al. (2011).

An interim analysis to assess futility analysis—and potential sample size re-estimation—will be conducted, as discussed in Section 5.1.

All results will be summarized descriptively by treatment arm and expressed as proportions, along with corresponding unadjusted/adjusted 95% CI of the difference between response rates, and p-values.

In the first step of multiple imputation, data will be multiple imputed using the FCS discriminant function separately by treatment arm to 20 imputed datasets. This analysis assumes data are missing at random. The imputation model will include the stratification factors, sex, baseline CRP, and a two-level binary factor (discharge from the hospital prior to discontinuing the study; Yes, No). [REDACTED]

For each imputed dataset, the proportion of subjects achieving the primary endpoint in the treatment arms will be compared using an adjusted risk difference obtained from the logistic regression model, adjusted for stratification factors, sex, and baseline CRP for each imputed dataset.

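### Entry now spans oxygen flows up to 10 LPM, but baseline oxygen is adjusted for only as yes/no; this forgoes some precision without biasing the result

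*Protocol*

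**What the plan says.** Protocol Version 3.0, section 4.1, criterion 7 requires a baseline saturation of at least 92%, "which can be either on room air or on oxygen supplementation if using" 10 LPM or less by nasal prong or close-fitting mask. In Version 2.1 the same criterion asked for at least 90% on room air and/or at least 94% "oxygen saturation on oxygen administration at 2 L/min by nasal canula at the baseline visit". The Version 3.0 summary of changes records the revision ("Baseline oxygen requirements in inclusion criterion 7 were changed based on clinical site feedback to oxygen saturation") and lists no change to stratification or covariates.

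Section 5.4.1 stratifies by age group and "requirement for oxygen at randomization (yes/no) at enrollment", the same as in Version 2.1 and in SAP 2.2.2. SAP 3.4.1.1 compares the arms with a risk difference from a "logistic regression model, adjusted for stratification factors, sex, and baseline CRP", and protocol 8.6 names the same covariates. The visible imputation text (SAP 3.1.8 and 3.4.1.1) uses those covariates plus a discharge indicator, and a redacted run follows it. The oxygen subgroup in SAP 3.4.4 is also yes/no.

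Oxygenation and FiO2 are scheduled at screening and Day 1 (protocol Table 1). Footnote 8 adds that "oxygen administration should also be recorded (eg, room air or oxygen flow by nasal canula or facial mask or endotracheal tube" are examples of what to record.

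**The concern.** One part of the primary endpoint is itself defined by oxygen flow: more than 15 LPM sustained for at least 48 hours (protocol 6.3.1). An entrant on 10 LPM starts about 5 L/min below that threshold, and one on 1 L/min starts more than 14 L/min below it. Both are coded yes. If risk rises with entry flow, the yes group now mixes unlike risks, and age group, sex and CRP separate them only as far as they happen to track flow.

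At stake is the precision of the primary comparison. The arms can differ by chance in mean entry flow, and the model as stated does not remove that part of the variation.

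**Working it through.** **1. The plan's own figure.** Inputs from protocol 8.1.1, 8.6 and 8.9: rates 0.30 and 0.18, 205 per arm, one futility look at 103 per arm (z = -0.67873), final boundary z = -1.91358. With unpooled variances, a bivariate normal calculation gives power 80.2% and one-sided alpha 0.0250. The stated 80% reproduces and is not in dispute.

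**2. The yardstick.** SE of the risk difference = sqrt[(0.30 x 0.70 + 0.18 x 0.82)/205] = sqrt(0.3576/205) = 0.0418, or about 4.2 points.

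**3. Validity.** Take 20% of subjects on room air (placebo risk 10%), 40% on low flow and 40% on high flow, with overall rates 30% and 18%. In 4,000 simulated trials per setting, the yes/no model and a three-level oxygen model both gave a mean risk difference of -0.119 to -0.121 under the planned effect. One-sided type I error was 0.023 to 0.030 for both (Monte Carlo SE about 0.0025). There is no bias and no inflation attributable to the yes/no coding.

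**4. Precision, linear flow (assumed inputs).** n = 410, 70 to 85% on oxygen, flows 1 to 10 L/min, log-odds slope 0.1 to 0.3 per L/min, 1,500 trials in each of 12 scenarios.
- The chance difference in mean flow between arms, among oxygen users, has an SD of 0.2 to 0.3 L/min.
- Each 1 L/min of imbalance moves the planned estimate by 1.1 to 5.1 points. With flow in the model it moves by -0.7 to +0.7.
- The ratio of variances, with flow to without, is 0.91 to 1.00. At the strong end this is worth 410/0.91 - 410 = 41 subjects, and at the weak end none.

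**5. Closed-form check of step 4.** Uniform flow on 1 to 10 has SD 9/sqrt(12) = 2.60. The SD of the arm difference is 2.60 x sqrt(4/287) = 0.307 with 70% on oxygen, and 2.60 x sqrt(4/348.5) = 0.278 with 85%. The shift per L/min is the oxygen share times the least-squares slope of risk on flow, averaged over arms. Intercepts are set to give 0.30 and 0.18, with room air placed at flow 0 on the same line.
- Slope 0.1, 70% on oxygen: 1.33 points per L/min; 1.33 x 0.307 = 0.41 points; (0.41/4.18)^2 = 1% of the variance.
- Slope 0.3, 85% on oxygen: 4.51 points per L/min; 4.51 x 0.278 = 1.25 points; (1.25/4.18)^2 = 9%.

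So the imbalance shift and the lost precision are one quantity seen two ways.

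**6. Three-level check.** With the mix in step 3 and a single look at one-sided 0.025, power with the yes/no factor is 83.3%.

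| Placebo risk, low / high flow | Power, three levels | Extra variance under yes/no |
|---|---|---|
| 35% / 35% | 83.3% | 0% |
| 30% / 40% | 83.6% | 0.7% |
| 25% / 45% | 84.4% | 3.1% |
| 20% / 50% | 85.7% | 7.2% |
| 10% / 60% | 90.0% | 23% |

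The last row is an extreme corner, with low-flow subjects at no more risk than those on room air. The three-level and closed-form calculations contain no CRP term. Any correlation between CRP and flow would shrink the gain.

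**The case against.** The strongest reply is that nothing is invalid. Randomisation protects the comparison, the standard error already allows for chance imbalance in flow, and adding a prognostic covariate is an efficiency choice. That stands, and it limits the point to an improvement. The covariate set was adopted after regulatory feedback (summary of changes, Version 2.0), and the SAP, which already reflects Version 3.0, kept it. So an oversight is not shown.

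The benefit is also unproven: the documents give no flow distribution, on-oxygen share or risk by flow. CRP is in the model and may absorb part of the difference. Recording of flow rests on a list of examples, with no numeric field shown.

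Several stronger readings are tempting but unsupported:
- That the amendment biases the primary result or raises type I error. Step 3 shows neither.
- That imbalance and lost precision are two separate harms. They are one, and the shift should be judged against the 4.2-point SE and not the 12-point target.
- That the amendment raised an explicit 2 L/min cap. Version 2.1 states saturation tests joined by and/or; the cap is an inference.
- That every on-oxygen entrant falls in WHO category 4. The scale gives no flow cut-off, and its instructions are in the Study Manual.
- That flow is absent from the imputation model. Part of that text is redacted.
- That distance to 15 LPM measures overall risk. Death and ventilation also count as events.

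**Conclusion.** The point holds as a cheap improvement to the primary analysis, not as an error. After Version 3.0, the only oxygen term in the stratification and the stated primary model does not distinguish entry flows up to 10 LPM among subjects alike in age group, sex and CRP. The cost is about 0 to 9% of the variance of the risk difference under the slopes assumed in step 4, and nothing if risk is flat in flow. Only the extreme row of step 6 goes beyond that range. The stated 80% power and the type I error are unaffected.

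**What to change.** Before the interim analysis and any unblinding:
- In SAP 3.4.1.1, add baseline oxygen flow (last recording before first dose, 0 for room air) as a pre-specified covariate in the primary logistic model, and keep the oxygen yes/no factor. State its functional form; a single linear term is the simplest.
- Add flow to the imputation model in SAP 3.1.8 and 3.4.1.1 if the redacted text does not already include it.
- State how missing baseline flow is handled, and confirm that the eCRF captures a value in L/min.
- In the SAP 3.1.7 non-convergence rule, remove sex before flow.
- List the departure from protocol 8.6 in SAP section 6.

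The cost is one degree of freedom and a documented change to the protocol's covariate list. Eligibility and randomisation are unchanged.

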4.2 Exclusion criteria

1. Inability to take oral medication at screening or baseline visit.
2. Evidence at screening or baseline of critical COVID-19 disease (eg, cardiac failure, septic shock or ARDS) or immediate need for intubation or mechanical ventilation per the judgment of the investigator.
3. Positive pregnancy test at screening for women of childbearing potential.
4. Lactating female at baseline for women of childbearing potential.
 - a. Note: a female will be considered eligible who is lactating at screening if she agrees to discontinue breastfeeding for the duration of the trial plus 14 days post last dose.
5. $\geq 5 \times$ upper limit of normal (ULN) for alanine or aspartate aminotransferases or total bilirubin $>1.5 \times$ ULN at screening or known history of Child-Pugh Class C, hepatitis B or C, or poorly controlled HIV infection. (Subjects with HIV infection who have normal CD4 counts may participate if they have been on a stable antiviral regimen for the 30 days prior to screening and are anticipated to remain on the regimen throughout the duration of the study.)
6. Glomerular filtration rate $<30 \text{ mL/min/1.73 m}^2$ at screening.
7. QTcF $>450 \text{ msec}$ for male or $>470 \text{ msec}$ for females or evidence of cardiac dysrhythmia at screening.
8. Significant history or evidence of clinically significant disorder, condition, current illness, illicit drug or other addiction, or disease that, in the opinion of the Investigator, would pose a risk to subject safety or interfere with the study evaluation, procedures, or completion.
9. Has been treated with immunomodulators or immunosuppressants including, but not limited to, interleukin (IL)-6 inhibitors, tumor necrosis factor (TNF) inhibitors, anti-IL-1 agents, and Janus kinase inhibitors, within 5 half-lives or 30 days, whichever is longer, prior to randomization, or plan to receive these agents any time during the study period.
10. Treatment with hydroxychloroquine/ chloroquine in the past 30 days or plan to receive these agents as part of investigational clinical trials or SOC any time during the study period.
11. Recent (within 30 days) or current participation in other COVID-19 therapeutic trials or expanded access programs.
12. Prior or current participation in COVID-19 vaccine trials.

